### **9.3.2. Investigator-Identified Rash Events of Special Interest**

All rashes, regardless of assess causality or severity are reported as events of special (EOSI) interest by investigators in a protocol defined manner. However, the endpoint of interest is the proportion of subjects with a treatment-emergent, treatment-related AE consistent with drug rash. These events are marked as EOSI on the AE eCRF page and will be referred to as investigator-identified drug rash.

For the investigator-identified rashes, separate listings will be provided. In addition, for investigator-identified rashes there will be a summary that shows, by treatment group, the number and percentage of subjects with:

- A TEAE

- A drug-related TEAE
- Permanent discontinuation from study drug due to the TEAE
- An AE that was considered an TESAE
- Any Grade 3 or higher TEAE
- Any Grade 3 or higher drug-related TEAE
- Any TEAE leading to interruption of study drug
- An TEAE that was considered a drug-related TESAE
- A TEAE that required use of concomitant medication

For treatment-emergent investigator-identified rashes, time to development of the AE will be estimated using the Kaplan-Meier method. The results will be displayed in summary tables as well as in a Kaplan-Meier plot. Subjects who do not experience the event of interest will be censored at the date of the last dose. Summary displays for the investigator-identified rashes will include a count of the number of AEs as well as the number of subjects who experience each AE.

A Kaplan-Meier plot and summary of duration of event will be provided for the investigator-identified rashes. The summary display will provide the median duration of event by treatment group, with the event as the unit of interest rather than the subject.

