Overall, 49.8% of subjects had at least 1 TEAE assessed as drug-related by the Investigator (ie, TEAEs possibly, probably, or definitely related to study drug). Most TEAEs were Grade 1 (mild) or Grade 2 (moderate) in severity. Overall, 15.0% of subjects experienced a Grade 3 or Grade 4 TEAE. The most common Grade 3 or Grade 4 TEAEs were HAE (attacks) (3.5%), ALT increased (2.6%), hepatic enzyme increased (0.9%), LFT abnormal (0.9%), and pneumonia (0.9%). All other Grade 3 or Grade 4 TEAEs occurred in 1 subject each. Overall, long term prior androgen use of ≥ 5 years and discontinuation of androgens within 2 weeks of BCX7353 initiation was correlated with a higher frequency of Grade 3 or Grade 4 liver-related TEAEs.

Overall, 13.2% of subjects experienced a treatment-emergent SAE. Treatment-emergent SAEs that occurred in > 1 subject were HAE attacks (12 subjects [5.3%]) and medical observation (3 subjects [1.3%]). Three subjects (1.3%) experienced 4 treatment emergent SAEs assessed by the Investigator as related to study drug; G3 gastroenteritis and Grade 2 hepatic enzyme increased (n = 1), G3 abnormal LFT (n = 1), and G3 abdominal pain (n = 1). The 2 subjects with the treatment-emergent SAEs of gastroenteritis, hepatic enzyme increased, and abnormal LFT discontinued study drug. No subjects experienced a TEAE that led to death.

Overall, 27 subjects (11.9%) interrupted study drug due to TEAEs. The most common TEAE that led to study drug interruption was HAE (attack) in 5 subjects (2.2%). Overall, TEAEs in the GI SOC led to study drug interruption in the greatest number of subjects; 8 subjects (6.3%) treated with BCX7353 150 mg and 2 subjects (2.0%) treated with BCX7353 110 mg. Overall, 6 subjects (2.6%) discontinued study drug due to a GI TEAE; 2 subjects (2.0%) and 4 subjects (3.1%) in the BCX7353 110 and 150 mg dose groups, respectively.

For this study, nonserious treatment-emergent rashes were considered EOSIs for Investigator reporting purposes. Overall, 8 subjects (3.5%) had rash EOSIs assessed by the Investigator as related to study drug but these rashes included non-specific urticaria and brief episodes of erythema. A total of 2 rash events were assessed by the Sponsor medical officer as likely related

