to BCX7353 and consistent with delayed-type drug hypersensitivity, i.e. a diffuse maculopapular rash with pruritus but no systemic or mucosal symptoms. These rashes were consistent with those reported in prior studies, resolving quickly with no reoccurrence with study drug continuation or re-initiation (if drug was held).

GI events were considered AEs of interest; however, they were not considered EOSIs for Investigator reporting purposes. Overall, 105 subjects (46.3%) experienced a GI abdominal TEAE and 6 subjects (2.6%) discontinued due to a GI abdominal event. The most common GI abdominal TEAEs were diarrhea (13.2%), abdominal pain (13.2%), and nausea (7.9%). No dose response was observed. Most events were Grade 1 or Grade 2 in severity. Two subjects (0.9%) experienced 3 serious GI abdominal events, abdominal pain in 1 subject and diarrhea and vomiting in the other subject. The event of abdominal pain was assessed as related to study drug but the diarrhea and vomiting were not because there was another more plausible etiology.

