8.3.2. Subject Discontinuation from Study Drug

A subject will be permanently withdrawn from study drug for any of the following bulleted reasons, which will be recorded in the source documents and CRF. When medically feasible, the Medical Monitor must be consulted prior to subject discontinuation. In all cases, subjects who prematurely and permanently discontinue study drug should complete all scheduled procedures for the end-of-study visit outlined in Table 3.

- Emergence of any laboratory abnormality or AE that in the judgment of the Investigator compromises the ability of the subject to continue study-specific procedures or it is considered not to be in the subject's best interest due to an altered benefit-risk profile
- Reoccurrence of treatment-emergent AST or ALT elevation $> 5 \times \text{ULN}$ (confirmed) if BCX7353 is restarted after meeting hold criteria as outlined in Section 12.2.2.
- Treatment-emergent ALT or AST $> 3 \times \text{ULN}$ combined with either laboratory abnormalities indicative of significant hepatic toxicity (ie, meeting Hy's law, total bilirubin $> 2 \times \text{ULN}$ OR with an INR > 1.5) or with symptomatology of acute hepatitis (ie, severe fatigue, nausea, vomiting, right upper quadrant pain and tenderness, fever, rash, and/or eosinophilia [$> 5\%$])
- Subsequent determination that inclusion/exclusion criteria were not met
- Intercurrent illness or emergence of a new illness/medical condition that would, in the judgment of the Investigator, affect assessments of clinical status to a significant degree
- Subject noncompliance with study drug or to the protocol
- Subjects with BCX7353-related Grade 3 or 4 rash as described by the Division of Microbiology and Infectious Diseases (DMID) criteria "skin-mucocutaneous" will be discontinued from study, if suspected to be due to BCX7353, and treated according to best medical practice. All subjects with a suspected drug rash should undergo specific rash evaluation as described in Section 11.1.12. A Grade 3 rash is defined as vesiculation or moist desquamation or ulceration, and a Grade 4 rash is defined as exfoliative dermatitis, mucous membrane involvement or erythema multiforme or

suspected SJS or necrosis requiring surgery. Subjects with a Grade 1 or 2 study drug-related rash may continue BCX7353 if the Investigator and subject deem it appropriate.

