11.1.13. Rash Assessment

Because of the potential for a study drug-related rash, all sites should be prepared to report details of suspected drug rashes and provide photographs.

Subjects should be medically evaluated for any diffuse maculopapular rash that could be drug-related. Rashes that resolve rapidly and therefore cannot be medically evaluated will not result in a protocol deviation. The site must enter the event into EDC as an AE (flagged as an EOSI) and inform the Sponsor Medical Monitor via the EOSI form of all BCX7353-related maculopapular rashes (Section [12.1.5.1](#)) after assessment. If the rash is assessed as not maculopapular (eg, urticarial) or not related to BCX7353 (i.e., has a clear alternative etiology), then the rash is reported as an AE, treated per Investigator judgement, and no further special assessment is required.

The following assessments must be completed for all subjects with a diffuse maculopapular rash assessed as related to BCX7353 as soon as logistically possible:

- Full dermatological exam to include the scope of the rash (location), vital signs, and mucosal examination. The notes documenting the examination should include detailed description of the rash; presence or absence of desquamation; presence or absence of blistering and if present, its extent; presence or absence of mucosal involvement and if present, its extent; and any other associated abnormal physical findings.
- Vital signs including temperature
- High resolution photographs taken to provide both detail regarding the rash (close-up) and details regarding the extent of the rash (whole body or body part). Cameras must be able to provide clear images taken in close proximity to the skin. The picture should include a ruler (centimeter) for scale. Every attempt to protect subject anonymity should be made.
- All detailed clinical information regarding the rash, examination, treatment and interpretation of the event needs to be reported on an SAE/Event of Special Interest (EOSI) report form as per Section [12.1.5.1](#).

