12.1.1.3. Adverse Events of Special Interest

For this protocol, non-serious treatment-emergent maculopapular rashes that are deemed related to BCX7353 will be considered EOSIs. This does not include other types of rashes such as urticaria or eczema. All treatment-emergent skin conditions should be reported as AEs but only maculopapular rashes deemed related to BCX7353 should be considered EOSIs.

An EOSI event in and of itself will not be considered serious unless it meets the seriousness criteria above. Events of maculopapular rash assessed as possibly, probably, or definitely related to BCX7353 regardless of severity must be reported to the Sponsor Medical Monitor as described in Section 12.1.5.1. Management of BCX7353 drug-related rash is provided in Section 11.1.12.

12.1.2. Method, Frequency, and Time Period for Detecting Adverse Events and Reporting Serious Adverse Events

Reports of all AEs and SAEs, regardless of Investigator attribution, are to be collected from the time of signing of the informed consent through to the last study visit (i.e., through the posttreatment end-of-study visit). All AEs and SAEs are to be reported on the AE CRF.

AEs should be documented on CRFs as Investigators become aware of them. AEs are to be followed until the event resolves. If an event is ongoing at the End of Study visit, Grade 1 and 2 events do not need to be followed if the event is deemed unlikely to be related or not related to study drug (see Section 12.1.3 for AE grading). For all Grade 3 and 4 events or events deemed at least possibly related to use of study drug, the event should be followed until the AE is resolved or the subject is in a clinically stable condition with regards to the AE.

The Investigator shall report all SAEs immediately to the Sponsor by communicating with the Medical Monitor (phone or email) and by submission of an SAE report form via email, and entering the event onto the AE CRF within 24 hours of their knowledge of the event (see Section 12.1.5). The SAE report form is a detailed, written report on the SAE provided by the Sponsor or designee. The Investigator should follow all unresolved SAEs observed during the

study until they are resolved, or are judged medically stable, or are otherwise medically explained.

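### The drug-rash endpoint depends on an EOSI mark that the SAP and the current protocol define differently, so pooling on the mark would mix two definitions

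*SAP*

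**What the plan says.** Protocol 7.1.1 names as a safety endpoint the proportion of subjects with a treatment-emergent, treatment-related adverse event (AE) consistent with a drug rash. The documents differ on which rashes carry the mark (event of special interest, EOSI) that picks these events out.

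- **SAP 9.3.2** starts from a broad rule: "All rashes, regardless of assess causality or severity are reported as events of special (EOSI) interest by investigators". It then defines the analysis set by the mark: "These events are marked as EOSI on the AE eCRF page and will be referred to as investigator-identified drug rash". The rash summary, the Kaplan-Meier analysis of time to rash and the duration summary all run on that set.
- **Protocol 5.2.2** (interim data) describes a similarly broad rule: "For this study, nonserious treatment-emergent rashes were considered EOSIs for Investigator reporting purposes". It reports 8 subjects (3.5%) with "rash EOSIs assessed by the Investigator as related to study drug but these rashes included non-specific urticaria and brief episodes of erythema".
- **Protocol 12.1.1.3** (current) is narrow. It covers non-serious maculopapular rash deemed related, and adds: "All treatment-emergent skin conditions should be reported as AEs but only maculopapular rashes deemed related to BCX7353 should be considered EOSIs". Protocol 11.1.13 agrees. A rash is an ordinary AE with no special assessment "If the rash is assessed as not maculopapular (eg, urticarial) or not related to BCX7353".
- **Protocol 13.3.5** still ties the endpoint to the EOSI mark, but gives papular as well as maculopapular rash as examples.

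The SAP's revision table stops at protocol version 5.0, and the SAP plans about 225 subjects. The current protocol plans about 475.

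**The concern.** The same box on the AE form means different things depending on the rule in force when the rash was recorded. A related urticarial rash counts toward the endpoint under the broad rule and not under the narrow one. The same holds for a related rash with the more severe features in protocol 8.3.2 ("A Grade 3 rash is defined as vesiculation or moist desquamation or ulceration, and a Grade 4 rash is defined as exfoliative dermatitis") if the investigator does not also call it maculopapular. Related maculopapular rash that is non-serious counts under either rule.

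If both groups are pooled on the mark, the reported proportion and the Kaplan-Meier curve answer neither question cleanly: how often any related rash occurs, or how often the specific hypersensitivity rash occurs. This matters because rash is a named endpoint for the primary objective, and protocol 5.7 lists it as one of two important potential risks. SAP displays are by dose and in total, with no split by protocol version. Versions 6.0 and 9.0 give 150 mg only (protocol synopsis), so the mix could fall more on the 150 mg column.

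**Working it through.** **1. The mark in each place**

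| Place | Rashes that carry the mark |
|---|---|
| SAP 9.3.2 | All, any causality or severity |
| Protocol 5.2.2 (interim) | Non-serious, treatment-emergent |
| Protocol 12.1.1.3 and 11.1.13 | Maculopapular and related to BCX7353 (12.1.1.3 adds non-serious) |
| Protocol 13.3.5 | Uses the mark; examples are maculopapular and papular |

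The SAP's rash summary has a drug-related row, which removes the causality part of the difference in that table. The rash-type part remains.

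**2. The interim figure**

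Protocol 5.2.2 gives 100 subjects at 110 mg and 127 at 150 mg, 227 in all. Related rash under the broad mark: 8/227 = 3.5%, as stated. The 8 are not split by dose, and the number that were maculopapular is not given.

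**3. An illustration of the mix**

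Assumptions:
- all planned subjects beyond the interim, 475 − 227 = 248, are at 150 mg under the narrow rule;
- the first 227 were recorded wholly under the broad rule;
- the true risk is the same at both doses and in both periods;
- k of the 8 interim subjects would have met the narrow rule. Because the 8 included urticaria and erythema, k is run from 0 to 7, which takes at least one subject to have had no qualifying rash.

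Formula: rate at 150 mg = (127 × 8/227 + 248 × k/227) / (127 + 248).

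- Broad part: 127 × 8/227 = 4.48 subjects.
- k = 0: 4.48/375 = 1.2%.
- k = 7: 248 × 7/227 = 7.65; (4.48 + 7.65)/375 = 3.2%.
- All subjects under the broad rule: 3.5%.

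With 100 later subjects under the narrow rule instead of 248, the range is 4.48/227 = 2.0% to (4.48 + 100 × 7/227)/227 = (4.48 + 3.08)/227 = 3.3%. The effect shrinks as fewer subjects fall under the narrow rule.

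**4. A separate matter: HAE attacks in the AE totals**

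Protocol 12.1.1.1 says HAE attacks are not AEs, but the interim counts them. On N = 227, 13.2% corresponds to 30 subjects, 15.0% to 34, and the 3.5% with Grade 3 or 4 HAE attacks to 8. The lower bound removes every subject with an HAE-attack event. The upper bound supposes that each also had another qualifying event.

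| Total | As reported | HAE attack | Lower bound | Range without HAE attacks |
|---|---|---|---|---|
| Serious AE | 30 (13.2%) | 12 | 18/227 | 7.9% to 13.2% |
| Grade 3 or 4 | 34 (15.0%) | 8 | 26/227 | 11.5% to 15.0% |
| Interruption | 27 (11.9%) | 5 | 22/227 | 9.7% to 11.9% |

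**The case against.** **The events are already tabulated.** SAP 9.3.1 plans drug-related treatment-emergent AEs by system organ class and preferred term, as subjects and percentages by dose. Protocol 12.1.1.3 requires every treatment-emergent skin condition to be reported as an AE. Related urticarial, vesicular or exfoliative rash therefore appears there whatever the mark, and a reader who infers that a rash signal would be hidden goes too far. This stands. What those tables do not give is one subject-level rash total, or a time-to-event analysis, on a uniform definition.

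**The mixing is conditional.** This SAP covers versions to 5.0 and about 225 subjects, and protocol 13.3 says a detailed SAP will be developed. A later SAP could settle the point. That also stands, but none is among the documents, and the current protocol's own analysis section still uses the mark.

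**The gap between the rules is not measured.** One might set 3.5% against the two interim events that the sponsor's medical officer judged likely related and "consistent with delayed-type drug hypersensitivity, i.e. a diffuse maculopapular rash with pruritus but no systemic or mucosal symptoms", and infer a four-fold or larger difference. The documents do not support that. The 8 are investigator assessments. The narrow mark is also set by investigators and includes possibly related rash. The comparison changes the assessor and the causality threshold as well as the rash type.

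**The dose direction is not established.** One might infer that the 150 mg rate will look lower than the 110 mg rate. The documents do not say which version narrowed the mark. Subjects who started on 110 mg stay on study, and under SAP 6.5.2 they remain in their Day 1 group even after moving to 150 mg. Their later rashes may also be recorded under the narrow rule.

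**A broad term list admits non-specific rash.** It does, which is why the narrower subset needs equal prominence.

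**Conclusion.** The inconsistency is real and worth correcting before database lock. The endpoint is tied to a mark whose scope differs between the SAP and interim on one side and the current protocol on the other, and protocol 13.3.5 does not match protocol 12.1.1.3. Pooling on the mark would give a named endpoint and a Kaplan-Meier analysis on mixed definitions.

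The cost is consistency and interpretability; the rash data themselves are kept. The size is unknown. The 1.2% to 3.2% range at 150 mg, against 3.5%, rests on all the assumptions listed with it and is not a forecast. An uneven effect by dose is possible, but its extent cannot be determined from the documents.

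The HAE-attack point is separate and of low priority. Attacks have their own preferred-term row, and the documents do not show what other protocol versions told sites to report. A subject-level total without attacks cannot be read from the preferred-term rows, because one subject may have several events.

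**What to change.** - **Reconcile the text.** Bring SAP 9.3.2 and protocol 12.1.1.3 and 13.3.5 into line on what the EOSI mark covers, including papular rash, and state in the SAP which rule applied under each protocol version.
- **Define the endpoint without the mark.** In SAP 9.3.2, define drug rash for all subjects as any treatment-emergent AE in a preferred-term list fixed before database lock and assessed as possibly, probably or definitely related, whatever its mark, seriousness or grade. SAP 9.3.3 and 13.3 already do this for gastrointestinal events. Run the summary and the Kaplan-Meier analysis on that set.
- **Keep the specific signal visible.** Report the maculopapular or papular subset beside it with equal prominence. Give the count of marked events by protocol version as supportive.
- **Optional and separate.** In SAP 9.3.1, keep the as-reported tables and add one supportive line each for serious AEs, Grade 3 or 4 AEs and interruptions that excludes HAE-attack terms.

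The cost is SAP and protocol wording, one term list and a few table lines. No new data are needed, since all treatment-emergent skin conditions are already reported as AEs. The drawback is two rash figures to explain, and the broader one will include some related urticaria or erythema.

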### **9.3.3. Gastrointestinal Abdominal-Related AEs**

Gastrointestinal (GI) abdominal-related AEs are also of interest, although these are not AEs of special interest for investigator reporting purposes. There are no appropriate standard MedDRA queries (SMQs) to evaluate abdominal-related AEs that are appropriate to assess potential adverse events associated with BCX7353 use. In order to create a list of PTs that are pertinent, the events to be analyzed have been prospectively defined as all PTs within the MedDRA 19.1 hierarchy under the High Level Group Terms (HLGTs) of 1) gastrointestinal signs and symptoms and 2) gastrointestinal motility and defaecation conditions (See Section 13.3 for a detailed list of PTs High Level Terms, and HLGTs). This selection is broad enough so that GI events are appropriately identified and analyzed but excludes terms that, although in the GI SOC, are not representative of the events of concern such as oral or esophageal events.

For the GI abdominal-related events, separate listings will be provided. In addition, for GI abdominal-related events there will be a summary that shows, by treatment group, the number and percentage of subjects with:

- A TEAE
- A drug-related TEAE
- Permanent discontinuation from study drug due to the TEAE
- An AE that was considered an TESAE
- Any Grade 3 or higher TEAE
- Any Grade 3 or higher drug-related TEAE

- Any TEAE leading to interruption of study drug
- An TEAE that was considered a drug-related TESAE
- A TEAE that required use of concomitant medication

For treatment-emergent GI abdominal-related AEs, time to development of the AE will be estimated using the Kaplan-Meier method. The results will be displayed in summary tables as well as in a Kaplan-Meier plot. Subjects who do not experience the event of interest will be censored at the date of the last dose. Summary displays for the GI abdominal-related TEAEs will include a count of the number of AEs as well as the number of subjects who experience each AE.

A Kaplan-Meier plot and summary of duration of event will be provided for GI abdominal-related TEAEs. The summary display will provide the median duration of event by treatment group, with the event as the unit of interest rather than the subject.

A separate analysis will be conducted in which the number and proportion of subjects with either a GI abdominal-related TEAE or subject-reported abdominal-only attack is presented. The number of events will also be included in the summary.

